7.4 Early Termination Procedures

Early termination assessments will include the full battery of neuropsychological testing, advanced MRI, and lumbar puncture to the extent that a participant is willing to undergo these follow-up assessments. The minimum assessment required for early termination is a clinical evaluation by the study physician to assess for patient safety and provide instructions to return the study drug.

7.5 Follow-up Visit (Day 90 ± 15)

At the 3-month follow-up visit, the following assessments will be performed and recorded in the participant's source documentation/medical record and on the CRF:

- Vital signs
- Weight
- Concomitant medications
- AEs
- Quick Dementia Rating Scale (QDRS)
- Clinical Dementia Rating (CDR) score, derived from QDRS
- Lumbar puncture to test for AB42 and Tau protein levels
- Advanced brain MRI
 - T1, T2, SWI, Neuromelanin, BOLD, ASL perfusion, DTI-NODDI, MRS of the precuneus
- Cognitive examination including:
 - Montreal Cognitive Assessment (MoCA)
 - Mini-mental Status Examination (MMSE)
 - Alzheimer's Disease Assessment Scale (ADAS-Cog12)
- Blood tests for:
 - Complete blood count + diff
 - Creatinine clearance
 - Thyroid hormone panel
 - Electrolytes
 - Inflammatory markers (hsCRP, TNF α , CD4, CD8, absolute neutrophils)

- Quantitative immunoglobulins
- Total and direct bilirubin
- Hemoglobin
- ProdromeScan blood test for:
 - Phosphatidylethanolamines
 - Choline
 - Mitochondrial function

Note: NE3107 was not teratogenic in rat and rabbit safety studies. Sexually active male and female patients on study should continue using barrier method contraception for 72 hours (three days) after the last dose of NE3107 (terminal plasma t1/2 6-8 hours). The outcome of any pregnancy conceived by a patient on study will be followed to term and the results (normal or detailed description of abnormalities) will be collected as part of the study data and reported to the primary IND holder (Biovie, Inc.).

8 QUALITY CONTROL AND ASSURANCE

BioVie Inc. is encouraged to visit The Regenesis Project at their convenience. The Principal Investigator (PI) and study staff will provide upon request source documents and/or other study-related documents. The PI will maintain regular written and telephone communication with BioVie Inc. In addition, to ensure quality data and standardization, The Regenesis Project will send monthly status reports to BioVie Inc.

All data will be recorded in accordance with good clinical practice (GCP) to ensure accuracy, completeness, legibility, and timeliness of the data reported. All data will be recorded directly on the source documents and will be considered source data. This data will be transferred to Case Report Forms (CRFs). Source data and CRFs will be kept on site at The Regenesis Project. All records and documents pertaining to the study will be retained by The Regenesis Project for at least five (5) years from the completion of the study and will be available for inspection by the Sponsor and Regulatory Agencies.

All source documents and laboratory reports will be Quality Control reviewed to ensure accuracy and completeness. Adverse events will be reviewed and assessed for severity according to the ICH SAE E2A, dated 27 October 1994, by the PI. Specific processes of the study, source documentation and case report forms, and any reports will be audited internally within The Regenesis Project and may be subject to audit by BioVie Inc.

9 PLANNED STATISTICAL METHODS

9.1 General Considerations

Statistical analyses will be performed by the statistician on staff with The Regenesis Project. Software for statistical analyses will include Microsoft Excel (version 14 or newer) and IBM SPSS Statistics for Windows, version 26 (IBM Corp., Armonk, N.Y., USA). Statistical analyses will be run to compare change from baseline at the post-intervention termination follow-up (three months after baseline) using a level of significance of 0.05.

A single unblinded interim analysis may be performed when 30% to 50% of the participants have completed the final follow-up timepoint. The purposes of this interim analysis are to declare futility, study discontinuation for overwhelming efficacy, or sample size re-estimation. The sample size will not be reduced based on interim data.

The primary analysis model for the efficacy endpoints will be an MMRM analysis. All available data will be included in these models with no imputation for missing data. Supportive analyses of efficacy data may be conducted to evaluate different methods of handling missing data (i.e., Last Observation Carried Forward, Baseline Observation Carried Forward, multiple imputation for missing data, etc.). These supportive analyses will be detailed in the SAP. Each endpoint within the neuropsychological testing family will be analyzed using MMRM analysis methods in a similar manner as to how the primary endpoints will be analyzed. Formal significance for a given hypothesis will only be declared if that hypothesis is significant and all hypotheses within the family preceding it are significant. This approach will ensure strong type 1 error control is present for all statistical tests conducted.

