3.3 Study Duration and Dates

The proposed participant recruitment start date will begin on 15 January 2022 and end on 31 January 2022. The recruitment period of 2 weeks, active treatment intervention period of 3 months, and final follow-up period of 2 weeks yields an expected 4-month study duration.

The actual overall study duration, start date and end date may vary depending on participant recruitment.

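### On the planned dates the optional interim falls after enrolment has closed and about 93-97% of treatment has been given, so stopping saves little, and the look has no alpha adjustment

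*Combined protocol and SAP*

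**What the plan says.** Section 9.1 of the combined protocol and SAP states: "A single unblinded interim analysis may be performed when 30% to 50% of the participants have completed the final follow-up timepoint." The stated purposes are "to declare futility, study discontinuation for overwhelming efficacy, or sample size re-estimation", and "The sample size will not be reduced based on interim data", so re-estimation can only go upward. Section 9.1 gives no futility or efficacy boundary, no division of alpha between the looks and no re-estimation rule. It sets the significance level at 0.05 and says that ordered testing within families secures strong type 1 error control for every test.

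On timing, section 3.3 states: "The proposed participant recruitment start date will begin on 15 January 2022 and end on 31 January 2022." After three months of treatment, a "final follow-up period of 2 weeks yields an expected 4-month study duration". The same section adds a caveat: "The actual overall study duration, start date and end date may vary depending on participant recruitment." Section 7.1 allows Days -10 to -1 for screening and baseline, and section 7.5 sets the final visit at Day 90 ± 15. Section 9.2 plans about 25 participants to leave 20 completers after 20% attrition. It says recruitment is not a limiting factor, and it gives no effect size, standard deviation or test for the power calculation.

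**The concern.** An interim analysis is worth its cost when something remains to be decided: participants not yet enrolled, treatment not yet given, or a sample size that can still be changed. Here a 16-day recruitment window is followed by a 90-day endpoint, and the trigger counts participants who have reached that endpoint. By the time 30% have reached it, the others are not far behind.

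The cost remains even when the benefit is small. An efficacy look with no boundary is a second chance to declare success at 0.05, which the ordered testing in section 9.1 does not address. That ordering handles several hypotheses at one analysis, not one hypothesis tested twice.

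**Working it through.** **Inputs.** Recruitment lasts 16 days, 15 to 31 January (3.3). Screening and baseline take 1 to 10 days (7.1). The final visit is at Day 90, window Day 75 to 105 (7.5). Enrolment is 25 (9.2). The trigger is 30-50% of 25, that is 7.5 to 12.5, taken as the 8th to the 12th completer (9.1).

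**The plan's own figures.** 20/(1 - 0.20) = 25 participants, as stated. 14 + 90 + 14 = 118 days, or 3.9 months, which matches the stated four months. The power calculation cannot be reproduced, because its inputs are not given.

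**Is everyone enrolled at the trigger?** The earliest possible final visit is day 1 + 75 = 76 after recruitment opens. Recruitment closes on day 16. The gap is at least 76 - 16 = 60 days under every permitted window.

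**Nominal schedule.** Assume 25 participants spread evenly over 16 days (spacing 16/24 = 0.667 day), final visit exactly at Day 90, no screening lag and no dropout. Total planned exposure is 25 × 90 = 2,250 person-days.

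| | 8th completer | 12th completer |
|---|---|---|
| Trigger (days from opening) | 7 × 0.667 + 90 = 94.7 | 11 × 0.667 + 90 = 97.3 |
| Days since recruitment closed | 78.7 (11.2 weeks) | 81.3 (11.6 weeks) |
| Last participant's treatment day | 79 | 81 |
| Person-days left | 0.667 × (1+...+17) = 102 | 0.667 × (1+...+13) = 61 |
| Exposure already given | 1 - 102/2,250 = 95.5% | 1 - 61/2,250 = 97.3% |

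For a fraction f completed, the lag from the trigger to the last Day 90 visit is (1 - f) × 16. That is 11.2 days at 30% and 8 days at 50%.

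**With screening lag and visit windows.** The check used 20,000 simulated trials with uniform entry over 16 days, uniform screening of 1 to 10 days and a uniform final visit on Day 75 to 105. The uniform distributions are an assumption. All 25 were enrolled at the trigger in every trial. Mean exposure already given was 93% (8th completer) and 97% (12th). The least advanced participant was on average at Day 75 and Day 80. The last final visit came on average 24 and 20 days later. The theoretical extreme is a last participant at Day (1 + 75) - (16 + 10) = 50.

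**What each purpose can achieve.**
- Futility or efficacy: either can be declared, but stopping saves no enrolment and about 3-7% of exposure. That is before any time for image processing, for which the documents give no figure. It is also before data checking, which section 10.10 ties to audits held at least twice a month.
- Re-estimation: new participants could be added only by reopening recruitment. The plan has no reopening procedure, no rule, and no stated effect size or standard deviation to re-estimate against.

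**Error rate.** Assume that the interim and final tests on one endpoint each use two-sided 0.05 (critical value 1.96), that the statistics are approximately bivariate normal with correlation √f, and that there is no binding futility stop. The chance of at least one false rejection is 1 - P(|Z1| < 1.96 and |Z2| < 1.96).
- f = 0.30, correlation 0.548: 0.089.
- f = 0.50, correlation 0.707: 0.083.

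**The case against.** The strongest reply is that the dates are only proposed and section 3.3 says they may vary, that the interim is optional, and that section 9.2 says recruitment is not limiting. Much of this stands. A reader might infer that none of the three purposes could be served. The documents do not support that: futility or efficacy can still be declared, and a larger sample can still be reached by reopening recruitment, which is undescribed but not ruled out.

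A reader might also take enrolment still being open as the test of usefulness. With even accrual, that needs more than about 127 days (8th completer) or 166 days (12th). It is the wrong test, because stopping can spare treatment well before then. With 60-day accrual, everyone is enrolled, but the last participant is only at about Day 48 to 58 and 10-17% of exposure remains. The low value of stopping therefore depends on recruitment staying close to plan.

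Nor do the documents show that the look can only do harm. Section 9.1 gives the analysis to a statistician on the site's staff and describes no firewall, but it does not say that raters would see interim results. The trial is single-arm and open-label, so there is no allocation to reveal.

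The reply does not remove the error-rate point, which holds whatever the dates. Making an unadjusted look optional does not control its error.

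**Conclusion.** The point holds as a limited one. On the planned dates, the interim comes about 11 weeks after recruitment closes (at least 60 days in any case), with about 93-97% of treatment given. The last final visit follows 8-11 days later on the nominal schedule, or 20-24 days later on average with screening lag and visit windows. Stopping then saves almost nothing, and re-estimation depends on a step that the protocol does not describe. An unadjusted look would raise the error on one endpoint from 0.05 to about 0.083-0.089, contrary to the control that section 9.1 claims.

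The timing result rests on the 16-day window, roughly even accrual and, for the wider figures, uniform distributions. The error figure assumes that both tests use two-sided 0.05; the plan does not say what level the interim would use. This is an inexpensive improvement to the plan, not a flaw that defeats the trial.

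**What to change.** Delete the interim futility and efficacy analysis from section 9.1, and state that efficacy data are analysed once, after the last 3-month visit. Safety stopping under section 9.6 is unchanged.

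The change is to one paragraph. Its real cost is the loss of the optional sample-size re-estimation. If the sponsor wants to keep that option, or if recruitment runs materially longer than planned, an interim should be reintroduced by amendment before any efficacy data are examined. The amendment should give the re-estimation rule, the procedure for reopening recruitment, the handling of alpha, and limits on who sees the results.

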9.2 Determination of Sample Size

Approximately 25 participants are expected to be enrolled in this Phase II trial to evaluate longitudinal findings from multimodal MRI among the population that is being studied. The study population is sufficiently broad and the conditions of interest are sufficiently prevalent so that recruitment of participants is not a limiting factor for the trial site.

The sample size was chosen according to a power analysis calculated with 80% power and a significance level of 0.05. To achieve completion data for at least 20 participants, enrollment of 25 participants will allow for 20% attrition while maintaining statistical integrity.

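### Section 9.1 credits ordered testing with strong type 1 error control for every test, but ordering does not cover the optional interim's efficacy stop or sample size increase

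*Combined protocol and SAP*

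**What the plan says.** Everything at issue is in section 9.1 (General Considerations). Tests of change from baseline are run "using a level of significance of 0.05", and no other level is given. On the interim, the section says "A single unblinded interim analysis may be performed when 30% to 50% of the participants have completed the final follow-up timepoint". Its aims are set out as "The purposes of this interim analysis are to declare futility, study discontinuation for overwhelming efficacy, or sample size re-estimation", with the limit that "The sample size will not be reduced based on interim data". Any re-estimation can therefore only keep or raise N.

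The section ends with the multiplicity rule: "Formal significance for a given hypothesis will only be declared if that hypothesis is significant and all hypotheses within the family preceding it are significant". It then concludes: "This approach will ensure strong type 1 error control is present for all statistical tests conducted".

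The one item that 9.1 defers to the SAP is the set of supportive missing-data analyses: "These supportive analyses will be detailed in the SAP". The multiple-comparison corrections in section 9.5.1 apply across voxels and between imaging analyses, not across looks.

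**The concern.** A fixed testing order protects a family only if each hypothesis in it is tested by a procedure that itself holds the stated level. Two features of the interim can break that condition. If the study may stop for efficacy at the look and otherwise tests again at the end, the same hypothesis has two chances of a false positive. If N is raised after seeing unblinded data and the final test ignores this, the final p-value no longer has its nominal distribution. Ordering addresses neither, and the supplied text lists no order.

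At stake is a stated property of the design. If the look is used, a result reported as significant at 0.05 may carry a higher error rate than 9.1 promises. The size of the excess depends on a bar and a re-estimation rule that the text leaves open, so they could be chosen with unblinded data in hand.

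**Working it through.** **The plan's own figure.** Section 9.2 states "To achieve completion data for at least 20 participants, enrollment of 25 participants will allow for 20% attrition while maintaining statistical integrity". Check: 20 / (1 - 0.20) = 25, which agrees. The 20 completers cannot be re-derived, because no effect size, SD, endpoint or test is given for the power calculation.

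**Inputs from the documents.** Level 0.05 and a look at 30-50% (9.1); 25 enrolled and 20 completers (9.2). This puts the look at 6 to 10 of 20, or about 8 to 12 of 25.

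**Assumptions, because the documents are silent.** One hypothesis, a two-sided test, final level 0.05, and a range of interim bars.

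**1. Efficacy stop, no change in N.** Under the null, the interim and final statistics Z1 and Z2 are bivariate normal with correlation √t, where t is the information fraction. With interim critical value c1 and final critical value 1.96, overall error = 1 - P(|Z1| < c1 and |Z2| < 1.96).

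| Interim bar | t = 0.3 | t = 0.4 | t = 0.5 |
|---|---|---|---|
| p<0.001 | 0.0505 | 0.0504 | 0.0502 |
| p<0.005 | 0.0531 | 0.0525 | 0.0519 |
| p<0.01 | 0.0567 | 0.0557 | 0.0546 |
| p<0.05 | 0.0893 | 0.0863 | 0.0831 |

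Simulated one-sample t-tests at these small numbers give about 8.4-9.2% for the p<0.05 bar, so the normal figure of 8.9% is not a ceiling.

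**2. Increase in N with an unadjusted final test.** For each interim value, take the total N between the planned N and 2N that maximises the conditional probability of crossing ±1.96, then average over the null distribution of Z1. This is a worst case; some re-estimation rules add nothing.

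| Efficacy stop | t = 0.3 | t = 0.4 | t = 0.5 |
|---|---|---|---|
| none | 0.0576 | 0.0599 | 0.0620 |
| p<0.001 | 0.0581 | 0.0602 | 0.0622 |
| p<0.05 | 0.0971 | 0.0963 | 0.0952 |

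**3. What a valid boundary would look like.** O'Brien-Fleming-type (Lan-DeMets) spending can be set up with 0.025 per side or with 0.05 in one function. The table gives the interim limit, with the final level in brackets. The last column is the smallest two-sided p that an exact Wilcoxon signed-rank test can return, 2/2^n for n completers.

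| Look | 0.025 per side | 0.05 in one function | Smallest Wilcoxon p |
|---|---|---|---|
| 6 of 20 | 0.00009 (0.0500) | 0.00035 (0.0498) | 0.0313 |
| 8 of 20 | 0.00079 (0.0497) | 0.00194 (0.0492) | 0.0078 |
| 10 of 20 | 0.00305 (0.0490) | 0.00557 (0.0478) | 0.00195 |
| 8 of 25 | 0.00015 (0.0500) | 0.00053 (0.0498) | 0.0078 |
| 10 of 25 | 0.00079 (0.0497) | 0.00194 (0.0492) | 0.00195 |
| 12 of 25 | 0.00243 (0.0492) | 0.00467 (0.0481) | 0.00049 |

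Under either form, a Wilcoxon stop is out of reach at 6 or 8 of 20 and at 8 or 10 of 25 (at 10 of 25 only just: 0.001953 against 0.001942). It is attainable at 10 of 20 and at 12 of 25. With 0.025 spent per side, 10 of 20 requires all ten changes to go the same way. Section 9.5.1 names the Wilcoxon test only for NAA:Cr and glutathione; the MMRM of 9.1 and the RMANOVA of 9.5.1 have no such floor.

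**4. Timing.** Section 3.3 plans recruitment from 15 to 31 January 2022 and three months of treatment; section 7.5 sets the final visit at Day 90 ± 15. The earliest final visit would be about 75 days after 15 January, that is 31 March, two months after recruitment closes.

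**The case against.** The strongest reply is that the effect is small where it is plausible. The plan speaks of overwhelming efficacy. Bars that fit the word, p<0.001 to p<0.01, give 5.0-5.7%, and the look is optional. The study has about 25 participants, one arm and no blinding (sections 4.1, 5.1.2, 5.5). On the section 3.3 schedule everyone is enrolled before the look, so an efficacy stop would save little, although that section lets the dates vary. All of this stands and limits the practical weight.

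A second reply is that a boundary may appear in a separate SAP. Section 9.1 refers to one, and it is not among the documents. That it sends only the missing-data analyses there does not prove that nothing else would be covered. But the assurance in 9.1 rests on the ordering rule itself, which could not deliver the control wherever a boundary is kept.

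A third reply is that the sentence also overreaches for other reasons: five MRI endpoints, unordered paired t-tests on secondary endpoints, and many correlations. That is fair, and the interim may be the smaller contributor, but it does not rescue the sentence.

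Two stronger readings are tempting. A reader might infer that the trial runs at 8-9% error. The documents do not support this, since those figures need p<0.05 as the interim bar and no bar is stated. A reader might also infer that the whole interim is invalid. It is not: a futility stop alone does not inflate type 1 error, and if the look is never taken this gap does not arise.

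**Conclusion.** The point holds as a defect in a stated property: 9.1 claims strong control for all tests from a rule that cannot cover a repeated look or a data-driven N, and nothing supplied fills the gap. Confidence is high about the gap in the text. The documents cannot show how much inflation would actually occur.

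For one two-sided hypothesis at final level 0.05, the excess runs from negligible under a strict bar to 9.5-9.7% in the extreme case of a p<0.05 stop combined with worst-case doubling of N. The upper part of that range is conditional on a loose bar that the wording of 9.1 does not suggest. This should be corrected because the correction is cheap, not because a large error has been shown.

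**What to change.** Delete the words claiming control for all statistical tests, limit the assurance to ordered hypotheses within a family, and list that order. In addition, choose one of the following.

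- **(a) Simplify.** Remove efficacy stopping and sample size re-estimation from 9.1, keep at most a non-binding futility or safety review, and test once at 0.05. The cost is an optional early look, which saves little on the planned schedule.
- **(b) Prespecify.** Before any look, name the interim endpoint and test, and fix an O'Brien-Fleming-type spending function at the actual information fraction. Add a capped re-estimation rule with a combination or conditional-error test. The final level becomes about 0.049-0.050 with 0.025 spent per side, or about 0.048-0.050 with 0.05 in one function. State at which completer counts a Wilcoxon stop is attainable if NAA:Cr or glutathione is the interim endpoint.

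Narrowing the sentence alone would make the claim accurate, but would leave the interim rules open. Option (a) is about a paragraph of wording; option (b) needs more text and a short design calculation.

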9.2 Determination of Sample Size

Approximately 25 participants are expected to be enrolled in this Phase II trial to evaluate longitudinal findings from multimodal MRI among the population that is being studied. The study population is sufficiently broad and the conditions of interest are sufficiently prevalent so that recruitment of participants is not a limiting factor for the trial site.

The sample size was chosen according to a power analysis calculated with 80% power and a significance level of 0.05. To achieve completion data for at least 20 participants, enrollment of 25 participants will allow for 20% attrition while maintaining statistical integrity.

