2 STUDY OBJECTIVES

2.1 Primary Objective(s)

Primary endpoints will involve a comparison of neurophysiological health as evaluated by multi-modal brain MRIs obtained at baseline and post-intervention termination (3 months). Specifically, multi-modal MRI endpoints will include: (1) An increase or stabilization in glutathione levels (as measured by magnetic resonance spectroscopy, MRS) compared to baseline. Patients with cognitive decline often show characteristic change in MRS or volumetric evaluation compared to age-matched controls (Kuhn et al. 2021); (2) Stabilized and/or improved dendritic density compared to baseline (as measured by diffusion tensor imaging, DTI-NODDI); (3) Enhancement of arterial signal compared to baseline (as quantified by arterial spin labeling, ASL). Patients with cognitive decline often have decreased perfusion in temporal parietal or frontal regions of the brain with ASL perfusion (Kuhn et al. 2021); (4) increased functional connectivity of the nucleus basalis of Meynert (NBM) with both hippocampi as well as between both hippocampi compared to baseline, as visualized by seed analysis of blood-oxygen level dependent (BOLD) imaging as well as (5) increased neurovascular coupling as visualized by BOLD compared to baseline.

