9.5 Statistical Analysis of Endpoints

Based on published annual progression rates ranging from 15-35%, the investigative team determined that this study subset could yield a proportional expected progression rate of 4-9% among study participants over the 3-month study duration. (Maioli et al., 2007; McKann et al., 2011; Amieva et al., 2009; Mitchell & Shiri-Feshki, 2009; Schmidtke & Hermeneit, 2008; Albert et al., 2011; Mashour et al., 2019). Statistical analysis for primary and secondary endpoints will utilize standard evaluations for categorical data.

Primary endpoints will involve a comparison of neurophysiological health as evaluated by multi-modal brain MRIs obtained at baseline and post-intervention termination (3 months). Specifically, multi-modal MRI endpoints will include: An increase or stabilization in glutathione levels (as measured by magnetic resonance spectroscopy, MRS) compared to baseline. Patients with cognitive decline often show characteristic change in MRS or volumetric evaluation compared to age-matched controls (Kuhn et al. 2021); Stabilized and/or improved dendritic density compared to baseline (as measured by diffusion tensor imaging, DTI-NODDI); Enhancement of arterial signal compared to baseline (as quantified by arterial spin labeling, ASL). Patients with cognitive decline often have decreased perfusion in temporal parietal or frontal regions of the brain with ASL perfusion (Kuhn et al. 2021); Increased functional connectivity of the nucleus basalis of Meynert (NBM) with both hippocampi as well as between both hippocampi compared to baseline, as visualized by seed analysis of blood-oxygen level dependent (BOLD) imaging as well as increased neurovascular coupling compared to baseline.

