By measuring free-water changes and the integrity of white matter tracts, DTI can indirectly measure changes caused by amyloid plaque deposition (Wen, Risacher, Xie, Li, Harezlak, Farlow et al., 2021; Alexander, Lee, Lazar & Field, 2007; Smith, Johansen-Berg, Jenkinson, Rueckert, Nichols, Miller et al., 2007). The post-NE3107 DTI metric [fractional anisotropy (FA) and mean, axial and radial diffusivity (MD, AD, RD)] image will be subtracted from the baseline image to produce change images (Fu, Shrestha, Sun, Wu, Luo, Zhang, et al., 2019). Neurite orientation dispersion and density imaging (NODDI) uses a three-compartment model to probe brain tissue microstructure: (1) Free Water Fraction (FWF) which estimates the extent of CSF contamination, (2) Neurite Density index (NDI) which quantifies the packing density of axons/dendrites, and (3) Orientation Dispersion index (ODI) which assesses the coherence of neurites (Fu et al., 2019; Zarei, Patenaude, Damoiseaux, Morgese, Smith, Matthews et al., 2010).

Limited literature using NODDI has been produced in-vivo in mild-cognitive impairment subjects, but the current results show it to be more sensitive/robust than traditional FA values (Fu et al., 2019). Similar to ASL, the three indexes will be compared between baseline/follow-up values. It would be expected that an increase in NDI and a decrease in ODI/FWF to correspond with an improvement in brain health (Fu et al., 2019). Here, an established tract-based spatial statistics (tbss) approach will be used to assess the relationship between voxel-wise changes in white matter integrity (Fu et al., 2019). Additionally, graph theory will be applied to quantify the effect of NE3107 on hippocampal connectivity and associate this effect with cross-sectional and longitudinal cognitive performance (Wen et al., 2021). Lastly, probabilistic tractography will be used to simulate white matter connectivity

between the hippocampus formations (Zarei et al., 2010) and Nucleus Basalis of Meynert. The baseline and follow-up will similarly be compared. Again, RMANOVA will compare pre-and post-NE3107 treatment and within group analyses will assess network predictors of response to NE3107 treatment. All imaging analyses will be corrected for multiple comparisons, both across voxel and between analyses.

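### The 80% power in section 9.2 makes no visible allowance for the multiplicity correction that section 9.5.1 requires across the five primary MRI endpoints

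*Combined protocol and SAP*

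**What the plan says.** Section 9.2 gives the basis for the sample size: "The sample size was chosen according to a power analysis calculated with 80% power and a significance level of 0.05". The target is stated as "To achieve completion data for at least 20 participants", with 25 enrolled to absorb 20% attrition. The section names no endpoint, effect size, standard deviation, test, sidedness or type of power, and no adjustment for multiple endpoints. Section 9.1 gives the same unqualified level for change from baseline: "using a level of significance of 0.05".

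Section 2.1 numbers five primary endpoints, opening with "Specifically, multi-modal MRI endpoints will include: (1) An increase or stabilization in glutathione levels". The others are dendritic density (DTI-NODDI), arterial signal (ASL), functional connectivity (BOLD) and neurovascular coupling (BOLD). The connectivity item holds more than one contrast.

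Section 9.5.1 says, once each in its DTI-NODDI, ASL and BOLD parts: "All imaging analyses will be corrected for multiple comparisons, both across voxel and between analyses". It gives neither the method nor the number of analyses to be corrected for.

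**The concern.** The stated inputs look like those of one before-after comparison tested at an uncorrected 0.05. The planned primary imaging tests are several, and each faces a stricter threshold once the between-analysis correction is applied. On that reading, the power quoted in 9.2 belongs to a different test from the one that will be reported.

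This matters because 9.2 is the only statement of what 20 completers can show. A reader who takes 80% at face value would treat a non-significant corrected MRI result as stronger evidence against an effect than the design supports. The mismatch is separate from the missing effect size: supplying an effect size alone would not resolve it.

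**Working it through.** **Inputs from the plan.** Power 80%, level 0.05, 20 completers, 25 enrolled, 20% attrition (9.2); five primary MRI endpoints (2.1); correction between analyses (9.5.1); single arm, change from baseline.

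**Assumptions, because the plan is silent.** Paired t-test, two-sided; 0.05 per test; 80% per endpoint; 20 completers just reach 80%; Bonferroni over five as the reference correction.

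**Step 1: the plan's own figures.** The attrition arithmetic reproduces: 20 / (1 - 0.20) = 25. The 80% can be neither reproduced nor refuted, since no effect size or standard deviation is given. It can only be inverted.

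**Step 2: implied effect.** With standardised mean change d, the paired t statistic has n - 1 = 19 degrees of freedom and noncentrality d√n. Power is the probability that |T| exceeds the critical value at 1 - α/2. At α = 0.05 the critical value is 2.093. Solving for 80% gives d = 0.66, with noncentrality 0.6604 × √20 = 2.954.

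**Step 3: same effect, stricter level.** Hold d = 0.66 and n = 20 and replace 0.05 with 0.05/k:

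| Analyses corrected for (k) | Level per test | Critical value | Power per endpoint |
|---|---|---|---|
| 1 | 0.05 | 2.093 | 80.0% |
| 2 | 0.025 | 2.433 | 69.7% |
| 3 | 0.0167 | 2.625 | 63.1% |
| 5 | 0.01 | 2.861 | 54.8% |
| 10 | 0.005 | 3.174 | 43.8% |

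Normal approximation for k = 5: Φ(1.960 + 0.842 - 2.576) = Φ(0.226) = 58.9%, the same picture. If all 25 participants complete, power at d = 0.66 and 0.01 is 69%. One-sided at 0.01 with 20 completers and the same d, it is 66%.

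**Step 4: less conservative corrections.** Simulation of 60,000 trials, five endpoints each with d = 0.66, n = 20, between-endpoint correlations 0, 0.3, 0.5 and 0.8. Average power per endpoint:

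| Method | Range over the four correlations |
|---|---|
| Bonferroni | 55% |
| Holm | 65-68% |
| Hochberg | 70-71% |
| Benjamini-Hochberg | 74-77% |

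The step-wise gains depend on all five effects being real; with only one real effect, Holm gives 55%. Benjamini-Hochberg controls the false discovery rate rather than familywise error, so it is the lenient end. None of these figures includes voxel-wise correction or the extra contrasts within the connectivity endpoint, both of which would lower power.

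**Step 5: what 80% would need.** At two-sided 0.01 with 20 completers, d must be 0.84. At d = 0.66, about 31 completers would be needed, which is 31 / 0.80 = 38.75, or 39 enrolled.

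**The case against.** The strongest reply is that 9.2 says too little to be contradicted. It does not say that 0.05 was per test or that 80% was per endpoint. If 0.05 was familywise, there is no mismatch. If 80% meant success on at least one of the five, the figure could stand: under Bonferroni at d = 0.66 that probability is 98%, 93%, 88% and 77% at correlations 0, 0.3, 0.5 and 0.8. Neither reading is excluded. But neither is stated, and a plain 80% beside a plain 0.05 is most naturally read as one comparison. If the sponsor meant something else, 9.2 still has to say so.

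A second reply is that the size of the loss rests on a method the plan does not name. That stands. The loss per endpoint could be 3 to 6 points (Benjamini-Hochberg, all effects real) or 25 (Bonferroni over five). The planned tests also vary: MMRM in 9.1 and 9.3, repeated-measures ANOVA in 9.5.1, and a Wilcoxon test for glutathione. The paired t-test is a stand-in for these.

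A reader might infer three stronger claims that the documents do not support:

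- **That the MRI endpoints lack 80% power whatever the effect size.** An endpoint with a true standardised change of about 0.84 or more keeps 80% at 0.01 with 20 completers. The loss is established only at the effect for which 80% was calculated.
- **That the ordered rule in 9.1 lowers MRI power as well.** The rule reads "Formal significance for a given hypothesis will only be declared if that hypothesis is significant and all hypotheses within the family preceding it are significant". Such a rule leaves the level at 0.05, and the first endpoint in the order keeps its full power. It also follows a sentence about the neuropsychological family, which is secondary, and no order is given for the MRI endpoints. The closing claim of error control for all tests does not settle whether it reaches them.
- **That the plan has a 45% chance of missing a real effect.** That is the complement of the Bonferroni-over-five case, not a property of the plan as written.

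**Conclusion.** The point holds conditionally. Section 9.2 shows no allowance for a correction that 9.5.1 makes mandatory for all imaging analyses. If 0.05 was per test and 80% per endpoint, with 20 completers just reaching that power, then power at the powered effect falls below 80% under every correction examined: about 55% with Bonferroni over five, about 65-77% with the step-wise methods when all five effects are real, and lower once voxel-wise correction is counted. The direction does not depend on the undisclosed effect size; the amount depends on the correction method, the number of analyses and the correlation between endpoints, none of which the plan gives.

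This is a mismatch between sections together with under-specification, not an error in a stated sum. The only numerical expectation in the analysis section, a "proportional expected progression rate of 4-9% among study participants over the 3-month study duration", is not tied to any MRI endpoint or to the sample size, so it cannot fill the gap.

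**What to change.** In 9.2:

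- State that the 80% applies to a single uncorrected before-after comparison at 0.05, and name the endpoint, effect size, standard deviation, test and sidedness used.
- Restate the power, or the detectable change, at the level left after the 9.5.1 correction, using the sponsor's own effect size and planned test. On the assumptions above, the detectable change for 80% power at two-sided 0.01 with 20 completers is about 0.84. That figure is illustrative and should not be copied in place of the sponsor's calculation.
- If 0.05 was familywise, or 80% meant at least one endpoint, say so and show the calculation.
- Remove the unqualified 80% claim for the primary MRI endpoints as a set.

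The restatement requires 9.5.1 to name the correction method and the number of analyses it covers.

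The cost is wording and a short recalculation, with no extra participants, scans or analyses. The downside is a less favourable stated power.
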